	
If necessary, collection of additional or incomplete data is carried out online/by telephone or at the subject's place if the subject permits.
 
Blood specimen testing was carried out at the Molecular Genetics Laboratory, Faculty of Medicine, Padjajaran University.
								
8.	Research Time Plan: ± 4 months	Starting: November 2023	Completed: February 2024						
9.	Data Collection Time Starting: November 2023 to February 2024								
10.	
Has This Protocol Been Submitted to Another Ethics Commission?
 
 
  Yes	 Accepted	
 
 If yes, attach a photocopy of the document!	
 
  No	
 
			 Yes	 Accepted	If yes, attach a photocopy of the document!		 No	
 Yes	 Accepted								
If yes, attach a photocopy of the document!									
 No									
11.	Allocation and Details of Research Funds (Human Resources, Consumables, etc.):								
	No.	Type of Spending	Component	Fee Required					
	1	Material	ATK	IDR 500,000					
	2	Material	Diet Procurement (20x3x30x45,000)	IDR 81,000,000					
	3	Material	Elisa Kit (IL-6; hs-CRP; adiponectin)	IDR 23,532,000					
	4	Material	DNA isolation kit (40x200,000)	IDR 8,000,000					
	5	Material	Primary (1x400,000)	IDR 400,000					
	6	Material	Primary Design Services (1x150,000)	IDR 150,000					
	7	Material	Subject Reward (40x35,000)	IDR 1,400,000					
	8	Data collection	FGD research preparation (5x105,000)	IDR 525,000					
	9	Data collection	Survey Officer's Honorarium (Screening: 40x8,000)	IDR 320,000					
	10	Data collection	Temporary Blood Glucose Test (40x18,000)	IDR 720,000					
	11	Data collection	Researcher Administration Honoraria	IDR 300,000					
	12	Data collection	Transport subject + officers (43x25,000x2)	IDR 2,150,000					
	13	Data collection	Data collection meetings (5x105,000)	IDR 525,000					
	14	Equipment Rental	Research Equipment (2x350,000)	IDR 700,000					
	15	Specimen Analysis	PCR Gene Amplification (42x100,000)	IDR 4,200,000					
	16	Specimen Analysis	Sequencing (42x350,000) + (42x10,000)	IDR 15,120,000					
	17	Specimen Analysis	Electrophoresis (42x50,000)	IDR 2,100,000					
	18	Specimen Analysis	Elisa Analysis (3x1,800,000)	IDR 5,400,000					
	19	Data analysis	Honor Data Processor	IDR 1,540,000					
	20	Data analysis	Meeting Consumption Costs (5x105,000)	IDR 525,000					
	21	Reporting and Output	International Seminar Fees	IDR 3,000,000					
	22	Reporting and Output	International Scientific Publication Fees	IDR 3,500,000					
		Total		IDR 155,607,000					

B. Clinical Trials

Research methods	
1.	
A summary of the research proposal includes the reason/motivation for conducting the research, the aims/objectives and benefits of the research, as well as the risks that may arise along with how to overcome them (written in language that is easy for non-doctors to understand):
 
Reason/Motivation for Conducting Research:
 
One nutritional strategy for obese individuals to lose weight is diet modification. Previous studies have shown that moderate weight loss (5–10% of initial body weight) achieved through lifestyle changes is associated with improvements in the cardiometabolic abnormalities characteristic of obesity (Espeland et al. 2007; Zomer et al. 2016). There have been studies and meta-


analyses that examine FTO gene polymorphisms coupled with certain types of dietary intervention which are then associated with changes in nutritional status, body composition, and various inflammatory and hormonal biomarkers in obese subjects (Razquin et al. 2010; De Luis et al. 2012b; De Luis et al. 2015a; De Luis et al. 2015b; Luglio et al. 2017; Di Renzo et al. 2018; De Luis et al. 2020; Parastouei et al. 2020), however, some things are still unclear and limited. Apart from that, no one has ever linked the FTO gene polymorphism to the Balanced Nutrition Diet intervention which is the reference in Indonesia, as well as its effect on cardiovascular risk.
 
Research purposes:
 
General purpose:
 
Examining the Effect of a Balanced Nutritional Diet on Cardiovascular Risk Factors Among Two Types of FTO rs9939609 Gene in Obese Young Women.
 
Special purpose:
 
 1. Analyze differences in the body composition of obese young women between A allele carriers (AC) and TT allele homozygous (TH) groups after Balanced Nutrition Diet intervention 2. Analyze differences in biomarkers of inflammation related to cardiovascular risk (interleukin (IL-6), high-sensitivity CRP (hs-CRP), and adiponectin (ADP)) of obese young women between A allele carriers (AC) and TT allele homozygous (TH) groups after Balanced Nutrition Diet intervention 
Benefits of research:
 
For research subjects, subjects can find out the allele type of the FTO rs9939609 gene themselves as an illustration of genes related to obesity and that can be used as a basis for precision nutrition interventions and will receive nutritional education about balanced nutrition. For the public, it is hoped that this research can increase knowledge about consumption recommendations, especially to normalize nutritional status and reduce the risk of cardiovascular disease by improving health status, especially for young adult women. For educational institutions, it is hoped that this research will provide new scientific evidence in the field of nutrigenomics regarding the interaction of genes and diet influencing the risk of obesity and cardiovascular disease. For the government, it is hoped that it can become a reference for making a policy to reduce obesity cases in Indonesia.
 
Number of Research Subjects:
 
This research uses a hypothesis testing formula for 2 independent samples based on Sastroasmoro & Ismael (2014):
 $n_1 = n_2 = 2 \left[\frac{(Z_{\alpha} + Z_{\beta})S}{X_1 - X_2} \right]^2$ 
The results of calculations using data from previous research (De Luis et al. 2015b) resulted in 7 people. This study used 4 groups, namely 2 control groups and 2 intervention groups, adding an anticipated dropout of 50%, the total number of subjects was at least 44 people or 11 people per group.
 
Information:
 
n = minimum number of subjects
 
Z_{α} = type I error (1.96)
 
Z_{β} = type II error (1.28; power 90)
 
S = standard deviation of the two groups
 
$X_1 - X_2$ = desired clinical difference (difference in weight between Allele T and Allele A)
 
Research by De Luis et al. (2015b) is a consideration for the expected weight loss of subjects in this study, namely assuming a weight loss of ± 1 kg in A allele carriers and ± 0.35 kg in homozygous T subjects after 1 month of intervention with the balanced nutritional diet provided.
 
How to Choose Research Subjects

--

	
Inclusion Criteria: 1) Obese women (body fat percentage >35%) who have light physical activity based on PAL (can select prospective subjects who have participated in preliminary research to completion); 2) Sundanese ethnicity (father, mother, grandfather, grandmother originally from West Java); 3) normal fasting blood pressure and blood sugar; 4) aged 18-25 years (based on Loos and Yeo (2014) that the relationship between the FTO gene and obesity is greatest in young adulthood); 5) not currently pregnant or breastfeeding; 6) willing to participate and sign informed consent.
 
Exclusion Criteria: 1) currently pregnant and breastfeeding; 2) have a history of chronic disease; 3) regularly consume antioxidant supplements and/or phytopharmaceuticals; 4) currently participating in other research.
 
Risks that may arise and how to overcome them:
 
Potential harm to the procedure being performed is very rare. The potential that may be encountered is limited to conditions of infection and the formation of hematomas (blood clots due to needle sticks). This risk can be reduced by treatment by experienced professionals and the use of disposable equipment and aseptic procedures, as well as appropriately sized needles to minimize the occurrence of hematomas. Apart from that, there may be a danger of bacterial contamination from intervention foods made by researchers. This can be prevented by maintaining hygiene and sanitation during preparation, processing, packaging, and when providing intervention food. In addition, the possibility of side effects or dangers from consuming the dietary intervention provided is prevented by collecting data on dietary restrictions/allergies for each subject before the intervention is carried out.
									
2.	
Research Methods (There may be more than one)  Randomization
 
 Open labelled  Placebo  Cross-over  Single Blind  Treatment controlled  Parallel  Double Blinds  Others mentioned,
									
3.	
New Drug Research (Investigational New Group=IND)/New Equipment (Investigational New Equipment =INE)/New methods or techniques:
 
 
  There isn't any	 There are:	 IND Reg No. POM: Name: Sponsor: Company name:	 INE Reg No. POM: Name: Sponsor: Company name:	Health Department Permit:  There is  No If there is, attach it	
 
 
Information About Try Ingredients:
 
a. Efficacy: – b. Security: –
					 There isn't any	 There are:	 IND Reg No. POM: Name: Sponsor: Company name:	 INE Reg No. POM: Name: Sponsor: Company name:	Health Department Permit:  There is  No If there is, attach it
 There isn't any	 There are:	 IND Reg No. POM: Name: Sponsor: Company name:	 INE Reg No. POM: Name: Sponsor: Company name:	Health Department Permit:  There is  No If there is, attach it						
4.	
For Genetic Research, Indicate Whether Genetic Engineering Techniques Are Used:
 
 No:  Yes, it has been reviewed  Recombinant DNA Advisory Committee  Biosafety Committee
									
5.	
This data is filled in if it concerns clinical drug trials
		Drugs Tested	Companion Medicine						
	a.	Generic name:								
	b.	Trade name:								
c.	Chemical name:									

	d.	Pharmacology class:			
	e.	Dosage form and drug strength:			
	f.	Packaging:			
	g.	Way of giving:			
	h.	Expired date:			
	i.	Batch Number:			
	j.	Analysis certificate:			
	k.	CPOB Certificate:			
	l.	Type and quantity of medicines to be imported:			
	m.	Manufacturer's name and address:			
	n.	Importer name and address:			
	o.	Distribution status of the test drug in other countries (if any, please attach it)			
	p.	Clinical trial phase:  Phase I  Phase II  Phase III  Phase IV			
	6.	How to Get Research Subjects:	 Individual contacts  Basic data from other studies  Reference  Advertisement (attach)  Others, explain		
	7.	Subject Criteria:	 Prone to  Child's age < 12 years  Prisoner  People with impaired cognitive function/unconsciousness  Pregnant mother  TNI and Police  Others, please specify:  Not Vulnerable		
8.	If this research is a clinical trial using human subjects, have pre-clinical trials/tests on animals been carried out, data on safety and efficacy from previous studies/in other countries?  No  Yes References (Name, Title, Journal): – Resume of Research Results: – Previous experience (own or others) of the action to be carried out (have clinical trials on humans been carried out, safety and efficacy data from previous studies/in other countries):  No  Yes References (Name, Title, Journal): Di Renzo L, Cioccoloni G, Falco S, Abenavoli L, Moia A, Sinibaldi Salimei P, De Lorenzo A. 2018. Influence of FTO rs9939609 and Mediterranean diet on body composition and weight loss: A randomised clinical trial NCT01890070 NCT. J Transl Med. 16(1):1–12. doi:10.1186/s12967-018-1680-7. Resume of Research Results: Randomized clinical trial examining the effects of FTO rs9939609 and the Mediterranean diet on body composition and weight loss. The results obtained show that the Mediterranean Diet is proven to be good for reducing body fat mass, while the data on the effects of FTO are still uncertain.				
9.	Clinical Trial Process a) Intervention administration (dose regimen, invasive and non-invasive procedures, comparison drugs, placebo): Following informed consent and initial screening, blood samples will be collected from all research participants to establish baseline data. Subsequently, randomization of the samples will				

	
be conducted using the block randomization method, based on the FTO gene allele. This process will involve two sample randomization blocks: one for A carriers allele and another for T homozygous individuals. Each block will then be randomized and divided into two groups, maintaining a 1:1 ratio between control and dietary intervention. Following randomization, four groups will be formed: two groups receiving the Balanced Nutrition Diet intervention (DAC: A allele carriers + Diet; and DTH: homozygous T allele + Diet), and two control groups (CAC: A allele carriers; and CTH: homozygous T allele). Nutrition education will be provided to all groups. The intervention period will span 4 weeks (28 days), after which a second blood draw will be conducted to gather endline data.
 
The Balanced Nutrition Diet is meticulously designed to supply the body with nutrients in suitable types and quantities, adhering to the principles of food diversity which include variety, balanced proportions, correct amounts, and consistency. Additionally, it emphasizes the "Fill My Plate" guideline, advocating for the consumption of all five food groups daily or at each meal. Portion sizes of the Balanced Nutrition Diet are structured according to the "Balanced Nutrition Tumpeng" model, encompassing 3-4 portions/day of carbohydrates, 2-3 servings/day of fruit, 3-4 servings/day of vegetables, and 2-4 servings/day of side dishes, with restrictions set at 4 tablespoons of sugar, 1 teaspoon of salt, and 5 tablespoons of oil per day, alongside a recommendation of drinking 8 glasses of water daily.
 
During the intervention period, food is provided three times a day - breakfast, lunch, and dinner - following a 28-day menu cycle. The researcher bears the sole responsibility for covering the cost of all food provided to the intervention group during this 28-day period. The Balanced Nutrition Diet offered adheres to specific macronutrient distribution ratios of 45-55% carbohydrates, 15-20% protein, and 20-25% fat, as outlined by Almatsier (2010). Complex carbohydrates, such as whole grains, are prioritized, while protein sources lean towards low-fat options, with half derived from plant-based sources. Monounsaturated and polyunsaturated fats are favored, and organic ingredients are preferred whenever possible.
 
Each meal's composition adheres to the "Fill My Plate" principle, and daily portions follow the "Balanced Nutrition Tumpeng" concept. Specifically, the diet provided by Eat & Fit Catering adheres to certain guidelines, including cooking methods that eschew fire and oil frying in favor of boiling, sautéing, or roasting techniques. Canola oil is the preferred oil, sodium-reduced salt is utilized, and mushroom stock serves as the primary flavouring agent, ensuring both healthfulness and taste. For each subject, energy requirements were calculated according to resting energy expenditure (REE) estimates using Mifflin-St. Jeor Equation (Mifflin et al. 1990). REE is then multiplied by the physical activity level (PAL) according to WHO-FAO that has been obtained.
 
REE (women)= (9.99 x Body Weight) + (6.25 x Height) + (5 x Age) – 161
 
The dietary distribution to subjects occurs three times, facilitated by couriers from the catering party. Should the delivery fall beyond the catering courier's radius, online delivery services will be utilized, with costs borne by the researcher.
 
In contrast, the control group subjects do not adhere to a specific diet regimen. However, they will receive general guidance on healthy eating habits and will be monitored closely. Nonetheless, their energy requirements will still be assessed based on REE and physical activity levels, as previously mentioned.
 
b) Determination of outcome indicators:
 
Evidence shows that compared with TT wild type, the risk allele A FTO rs9939609 showed significantly higher body weight, body mass index, waist circumference, hip circumference, and waist-to-hip ratio (Mangge et al. 2011; Tupikowska-Marzec et al. al. 2019; Mehrdad et al. According to Chrostowska et al. (2013), evidence is growing that the waist-hip circumference ratio is a stronger indicator of cardiovascular disease than body mass index. The meta-analysis of Gholamalizadeh et al. (2020), showed that carriers of the A allele of the FTO rs9939609 polymorphism had a higher fat percentage. The research results of Dorling et al. (2021) showed

--	---

	
the FTO SNP rs9939609 was associated with changes in REE adjusted for fat mass and lean mass, with the AA allele showing a decrease compared to TT.
 
Several studies have been conducted looking at the relationship between the FTO rs9939609 genotype and interleukin-6 (IL-6) levels, but only a few have shown real differences (de Luis et al. 2012b; Zimmermann et al. 2011; de Luis et al. 2016; Magno et al. 2018; Hosseini et al. 2011). Studies have also been conducted that there is an association of FTO rs9939609 with higher levels of C reactive protein (CRP) (Fisher et al. 2009; Sun et al. 2010; Lappalainen et al. 2011; Tupikowska-Marzec et al. 2019). However, other studies show contradictions (Zimmermann et al. 2011).
 
Research by Mehrdad et al. (2020a) showed that subjects with A allele carriers (AA and AT) had lower adiponectin levels than wild-type subjects (homozygous TT) with homozygous AA allele types having the lowest values although not significantly different. Several other studies also show the same thing in both obese and other types of adult subjects (Saucedo et al. 2017; Isgin-Atici et al. 2021). However, research by de Luis et al. (2016) and Duicu et al. (2016) showed a contrast, namely that adiponectin levels were lower in the TT genotype group compared to the AA genotype group. Based on what has been explained above, several outcome indicators that will be analyzed are waist-hip circumference, mass and total fat percentage &visceral, interleukin-6 levels, hs-CRP levels, and adiponectin levels.
 
Statistical analysis
 
The data obtained were tested statistically using SPSS statistical software for Windows (IBM version 26.0, SPSS Inc., Chicago, Ill., USA). The normality of variable distribution was verified with the Shapiro-Wilk test. Analysis of Variance (ANOVA) was used for all baseline data. Paired samples t-test was used to see changes in calorie intake, macronutrients, BW, BMI, waist circumference, hip circumference, waist-hip ratio, RM, percent total fat, visceral fat, subcutaneous fat, skeletal muscle, IL-6, hs-CRP, and adiponectin between before and after intervention. Data are presented as mean \pm SD and P < 0.05 was considered statistically significant.
 
c) Planned interim analysis: There is no interim analysis in this study.
 
d) Clinical trial termination procedures: Referring to the guidelines for good clinical trials in Indonesia (POM RI 2016), clinical trials are terminated if clinical trial safety problems occur, such as serious undesirable events and serious side effects of the test product. The principal investigator will report the KTDS to the ethics committee no later than 3 days after the incident is discovered. The possibility of KTDS that could occur in this study is that the patient requires hospital treatment as a result of the intervention process.
 
e) Estimated research time required for one subject per procedure: \pm4 weeks
 
f) Ethical issues (state your opinion about the ethical issues this research may encounter):
 
 • Respect for person (respect for human dignity): Subjects in this study took part based on their own conscious choice, there was no element of coercion. Subjects have the right to be protected, including that all Subject data will be kept confidential. • Beneficence(beneficial) Non-maleficence (not harmful): This research optimizes benefits and minimizes harm to subjects. The results of the research will be useful for society. The research design has been made as clear as possible. Researchers have competencies that are appropriate to the research topic to be conducted. • Justice(justice): Subjects are treated the same/or there is no differentiation between subjects.
--	--

	There is no conflict of interest
10.	
Adverse Event reporting plan(AE)
 
a. Recording (What will be reported): Each incident must be recorded in detail regarding the time it occurred and the causes to avoid similar incidents and as additional data for research progress reports.
 
b. Analysis and action procedure:
 
 1. Anthropometric Measurements After an overnight fast for 12 hours, all subjects underwent anthropometric evaluation. All individuals were instructed to remove their shoes and wear as light clothing as possible before undergoing measurements. Body weight, mass & percent body fat were measured with a Bioelectrical Impedance Analyzer (BIA). Body height was evaluated using a stadiometer to the nearest 0.1 cm. BMI is calculated using the formula = body weight/height² (kg/m²). Waist circumference and hip circumference were assessed using a flexible steel metric tape to the nearest 0.5 cm. The waist-to-hip ratio (WHR) was analyzed and evaluated according to clinical risk thresholds, equivalent to WHR > 0.9 for men and WHR > 0.85 for women. 2. Blood Sample Analysis A venous blood sample of around 6-10 cc is taken using a sterile syringe by competent licensed medical personnel. The blood is then divided into two different sterile tubes (Vacutainer®). The first tube is a purple cap tube containing EDTA, while the second tube is a yellow cap tube containing separator gel. After that, the sample is put on ice to be immediately taken to the testing site. The samples in the purple tube will then be processed for DNA and RNA isolation. DNA isolates were used for analysis of FTO gene variants using PCR and sequencing. Blood samples in yellow tubes were used for analysis of serum levels of interleukin-6, hs-CRP, and adiponectin using the ELISA method. All blood analyzes will be carried out at the Molecular Genetics Laboratory, FK UNPAD. The remaining samples were stored at -80 °C to be retested if necessary. 
c. Emergency request system: Each subject will be given a contact for researchers and doctors who can be contacted if there are complaints of illness related to the intervention. Researchers and doctors can be contacted 24 hours during the research period regarding interventions for emergency response preparedness. If there is an emergency, the subject will be taken to the emergency room at Hasan Sadikin Hospital.
 
d. Termination of subjects in research due to adverse events: If an undesirable event occurs, it must be immediately reported to the researcher. Researchers will then coordinate with parties who feel it is necessary to carry out follow-up as soon as possible. Then the researcher will assess whether the subject needs to be discontinued in the study after consulting with a clinical trial expert.

11.	
If this research uses human subjects, are the costs of dealing with side effects the responsibility of this research?  No  Yes
 
 - If yes, post-research responsibilities (capacity building, benefits to local community, continuation of therapy on the subject, etc.) - Is the subject insured?  Yes 
If "yes" please state the insurance institution: – Duration of Insurance and/or responsibility of the researcher towards the subject? –

12.	If we use biological samples, will they be sent overseas?  No  Yes, please state the destination country and attach itdraftsMaterial Transfer Agreement (MTA)!

C. Process of Obtaining Approval After Explanation (INFORMED CONSENT)/Informed Consent (IC)

1.	To Whom INFORMED CONSENT Is Explained(There may be more than one answer):	 Individual	 Group	 Guardian
2.	a. Who explains?	Principal Researcher		
	b. When will it be explained?	Before INFORMED CONSENT screening and signing is carried out		
	c. Are subjects given enough time to make a decision?	Yes		
	d. Who signed the INFORMED CONSENT?	The prospective subject itself		
	e. Who witnessed the INFORMED CONSENT signing?	Research assistant (doctor/nurse/midwife/nutritionist)		
3.	Ethical problems that the subject may face			
	a. Research risks			
	1. Disrupts routine health service activities	 Yes		 No
	2. Causes side effects on the subject	 Yes		 No
	3. Contrary to norms and customs local	 Yes		 No
	4. Economic losses and stigmatization occur subject	 Yes		 No
	b. Benefits of taking part			
	1. New knowledge increases	 Yes		 No
	2. Get health services	 Yes		 No
	3. Incentives	 Cash  No  Goods/Souvenirs		
	4. Compensation	 Insurance  Cash  No  Etc		
	c. Excessive influence (coercion)			
	1. Relationship between Chief Researcher and subject	 No		 There is
	2. If there is:	 Doctor-patient	 Teacher/lecturer-pupils/students	 Superiors and subordinates  Etc
	d.	
 • If the study uses healthy people, explain how the health checks will be carried out: – • If the study uses sick people, explain how to diagnose and name the doctor responsible! This study used young adult female subjects who were obese. The diagnosis of obesity is assessed by a nutritionist based on the percentage of total body fat > 35%. Responsible doctor: dr. [name], M.Pd., AIFO. ([name]). 		

D. Fill in the Consent Information After Explanation (INFORMED CONSENT)/Informed Consent (IC)

1.	Is the Narrative in Agreement After the Subject Explanation Explaining About:			
	a. Research summary information	 Yes	 No	
	b. The treatment applied to the subject	 Yes	 No	 Not Available
	c. Benefits for the subject	 Yes	 No	 Not Available
	d. Potential danger	 Yes	 No	 Not Available
	e. Right to resign	 Yes	 No	 Not Available
	f. Incentives for subjects	 Yes	 No	 Not Available
	g. Type of incentives provided	 Yes	 No	 Not Available
	h. Compensation for subjects	 Yes	 No	 Not Available

2.	Specimen Collection (Statements 2b-2d are filled in if the answer to 2a is "yes" and 2f-2g if the answer to 2e is "yes")		
	a. Was a specimen taken from the subject?	 No	✓ Yes, Blood
	b. Is there information on the number of specimens taken?	✓ Yes	 No
	c. Is there any information about the frequency of collection?	✓ Yes	 No

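### The stated minimum of 44 women is not matched by the itemised resources (40, 42 and 20 on diet), and neither 40 nor 44 gives 90% power after the stated 50% dropout

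*Combined protocol and SAP*

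**What the plan says.** Section B.1 (Number of Research Subjects) applies a two-sample formula with Z values of 1.96 and 1.28 (90% power). The calculation "resulted in 7 people". The text continues: "This study used 4 groups, namely 2 control groups and 2 intervention groups". After "adding an anticipated dropout of 50" per cent, it concludes that "the total number of subjects was at least 44 people or 11 people per group". The expected weight losses are about 1 kg in A carriers and 0.35 kg in TT women. The SD is defined but given no value.

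Section B.9(a) randomises 1:1 to diet or control within each genotype block, with three meals a day for 28 days.

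The funds table (item 11, Allocation and Details of Research Funds) itemises:

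- 40: "DNA isolation kit (40x200,000"), "Honorarium (Screening: 40x8,000"), "Subject Reward (40x35,000") and the blood glucose test
- 42: PCR, sequencing and electrophoresis
- 43: transport, subjects and officers together
- 20 on diet: "Diet Procurement (20x3x30x45,000")

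Neither section explains the difference.

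**The concern.** The same document gives two planned sizes. Four lines at 40 and a diet line at 20 look like a working size of 10 per group, while B.1 calls 11 per group a minimum. Randomisation is within genotype, so every randomised woman needs a DNA isolate and a genotype result. Counting 40 screenings for a target of 44 also leaves nothing for screen failures, although B.1 applies body-fat, ethnicity, blood-pressure, glucose and chronic-disease criteria.

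What is at stake is the trial's stated size and power. A reader of the eventual report could not tell whether 40 women would be full recruitment or a shortfall of 4. The 90% is also attached to a number of completers that the plan's own dropout figure does not leave.

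**Working it through.** **1. Reproduce the 44.** Inputs from B.1: base n = 7 per group, dropout 50%, four groups.

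- Multiplying: 7 x 1.5 = 10.5, rounded up to 11; 11 x 4 = 44. This matches.
- Dividing by the retained fraction: 7 / 0.5 = 14; 14 x 4 = 56. This does not match.

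So the plan added dropout by multiplication. At 11 per group with 1:1 allocation, 22 women are on diet.

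**2. Compare the resources with 44.**

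| Item | Counted | Needed for 44 | Short by |
|---|---|---|---|
| DNA isolation, screening, glucose tests, rewards | 40 each | 44 each | 4 each |
| PCR, sequencing, electrophoresis | 42 each | 44 each | 2 each |
| Meals, 28 days | 20 x 3 x 30 = 1,800 | 22 x 3 x 28 = 1,848 | 48 |
| Meals, 30 days | 1,800 | 22 x 3 x 30 = 1,980 | 180 |

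Transport (43) mixes subjects and officers. ELISA is priced without a per-woman count, so neither can be compared directly. The 22 lines sum to IDR 155,607,000, exactly the stated total, so the lower counts are built into the budget.

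**3. Cost of the gap at the plan's own unit prices, excluding transport and ELISA.**

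- Lines at 40: 4 x (200,000 + 8,000 + 18,000 + 35,000) = IDR 1,044,000.
- Lines at 42: 2 x (100,000 + 360,000 + 50,000) = IDR 1,020,000.
- Meals: 48 x 45,000 = IDR 2,160,000 for 28 days, or 180 x 45,000 = IDR 8,100,000 for 30 days.
- Total: IDR 4,224,000 (4,224 / 155,607 = 2.7%) or IDR 10,164,000 (6.5%).

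**4. Back-solve the SD.** From n = 2[(1.96 + 1.28)S / 0.65]², S = (0.65 / 3.24) x √(n/2). If 7 was reached by rounding up, the unrounded n lies above 6 and up to 7:

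- n = 6: 0.2006 x √3 = 0.348 kg (0.3475 before rounding)
- n = 7: 0.2006 x √3.5 = 0.375 kg

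**5. Power after 50% dropout.** Two-sided 5% two-sample t-test, noncentrality (0.65 / S) x √(n/2), df = 2n - 2:

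| Completers per group | S = 0.375 kg | S = 0.348 kg |
|---|---|---|
| 5 (40 randomised) | 67% | 74% |
| 5.5 (44 randomised, average) | 72% | 79% |
| 6 (44 randomised, upper) | 77% | 83% |
| 7 (the plan's base n) | 84% | 89% |

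The last row is below 90% because the plan's formula uses normal rather than t quantiles. Going from 7 to 5.5 completers, which is the effect of multiplying by 1.5, costs about 10-12 points. Going from 5.5 to 5, which is the effect of 40 rather than 44, costs about 5.

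**6. Dropout that still leaves 7 per group.** At 10 per group: 1 - 7/10 = 30%. At 11 per group: 1 - 7/11 = 36%. Both are below the anticipated 50%.

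**The case against.** The strongest reply is that the funds table is a costing and not an enrolment rule. Nothing in it limits recruitment, and B.1 says at least 44. The gap is a few per cent of the budget, and women who drop out use fewer meals. This stands. A reader might infer that 44 cannot be delivered, or that the trial will run with at most 10 per group; the documents support neither.

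Three further replies also have force.

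- The budget is not a coherent plan for 40. Among the genotyping steps only DNA isolation is at 40; the later steps are at 42. Reading 40 as the true enrolment would be selective. This adds a mismatch inside the table and does not remove the one with B.1.
- The meal line looks like 20 women, but 1,800 meals at 84 per woman (3 x 28) cover 1,800 / 84 = 21.4 women, so 21 in full. Over 28 days the shortfall is less than one woman's supply.
- B.1 allows women who completed preliminary research, and B.6 ticks data from other studies as the recruitment source. That may reduce new screening or genotyping, but the documents do not say by how much. It is therefore not shown that 40 budgeted screenings rule out 44 randomised women.

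Two more inferences should be resisted. The first is that the whole fall from 90% to 67-74% follows from counting 40: at 44 the power is only 72-79%, so most of the loss has another source. The second is that 40 makes equal genotype groups unlikely. At an assumed 50% carrier share, an exact 20/20 split of 40 has probability 12.5% and an exact 22/22 split of 44 has 12.0%, so this does not distinguish the two sizes.

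**Conclusion.** The inconsistency is real and can be checked from the text: a minimum of 44 (22 on diet) in B.1, against 40, 42 and a diet count of 20 in the funds table. It leaves the planned size unclear by up to 4 women (4/44 = 9%) and funds no margin for screen failures. It does not show that the trial is infeasible.

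The stated 90% power is not reached after the stated 50% dropout at either size. The power figures rest on three assumptions: an SD of 0.348-0.375 kg inferred from n = 7, a two-group contrast of 0.65 kg, and the 50% dropout taken literally and spread evenly over the groups. A larger SD would lower them.

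**What to change.** Make B.1 and the funds table agree, by one of two routes:

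- **Keep 44.** Raise every per-woman count to at least 44 (22 on diet) and add a stated screening margin. At the plan's own prices this costs about IDR 4.2 to 10.2 million (2.7% to 6.5%), before transport, ELISA and the screening margin. If preliminary-research participants reduce the number of new screenings or genotypes needed, say by how many.
- **Restate the size as 40.** Give 10 per group in B.1, and bring the lines at 42 into agreement or explain them.

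Under either route, state the SD used, the expected completers and the resulting power. On the assumptions above these are about 5 per group and 67-74% at 40, or 5 to 6 per group and about 72-79% (at 5.5) at 44. Replace these figures once the actual SD is given. The 30 days in the meal line and the 28 days in B.9(a) must also be reconciled.

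Restating size and power is a change of wording only, though the stated power becomes less favourable. Keeping 44 needs the small budget increase as well.
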